### 5.3.4 Examination of Subgroups

The co-primary and secondary efficacy endpoints, treatment-emergent adverse events, treatment-emergent markedly abnormal laboratory values will be examined for the following subgroups:

- On AChEI at baseline (Yes or Not)
- Region (US, Europe, Japan)
- Receiving memantine at baseline (Yes or No)
- AChEI and/or memantine at baseline (none, AChEI only, memantine only, AChEI+memantine)
- Hoehn & Yahr stage (0&I&II or III)

In addition, the co-primary and secondary efficacy endpoints will also be examined by the following subgroups:

- Baseline MMSE subgroup ( $\geq 14$  total score  $\leq 19$ ,  $\geq 20$  total score  $\leq 26$ )
- Age ( $< 65$ ,  $\geq 65$  to  $< 80$ ,  $\geq 80$ )
- NPI hallucination sub-item score ( $\geq$ median/ $<$ median)
- Caregiver's time per week to spend with subject ( $\geq$ median/ $<$ median)

For other demography and safety data (vital signs, ECGs, etc), the summaries will be subgrouped by stratification factors, as appropriate.

Where subgroups are small, summaries and analyses will be produced, caution will be used in the interpretation of those subgroups.

### 5.3.5 Handling of Missing Data, Drop-outs, and Outliers

#### 5.3.5.1 Efficacy

For non-EMA registration, for primary and secondary efficacy endpoints, there will be no imputation of missing value. MMRM and GLMM will be used to analyze repeated measures of continuous and ordinal data, respectively.

For EMA registration, for co-primary efficacy endpoint MoCA and all continuous secondary efficacy endpoints, there will be no imputation of missing value at individual level. The statistical estimate will be calculated based on the mean imputation method proposed by Mehrotra et al (2017). For EMA registration, the missing co-primary efficacy endpoint CIBIC-Plus and ordinal secondary efficacy endpoint will be imputed using control-based pattern imputation at subject level (Yuan 2014).

The date of change in AChEIs stable dose during treatment period, Screening and 12 weeks prior to Screening will be used in the sensitivity analysis to determine the censoring time. In case the date of change in AChEIs stable dose is missing, the missing date will be imputed similarly to missing start date of concomitant medication but replacing the First Dose Date by Last Visit Date before the change in AChEIs stable dose as reference date in the imputation. Please refer to AChEIs Stable Dose CRF page to determine the last visit date before the change in AChEIs stable dose. Where non-AChEI restricted medications are changed during the treatment period, Screening and 4 weeks prior to Screening (12 weeks prior to Screening for memantine), the above method will be used similarly.

Post-ED data will be included in all the analyses.

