- If a subject is already receiving AChEI at Screening, then they must be on a stable dose for at least 12 weeks before Screening and remain on the same dose during the study until the Follow-Up Visit.
- If a subject is not already receiving AChEI at Screening, then these should not have been used for at least 12 weeks before Screening and AChEI should not be started during the study until the Follow-Up Visit.
- As far as it is feasible subjects who start AChEI or change their dose of AChEI during the study should undertake an *Unscheduled Visit* before making such changes in their AChEI medications to undertake efficacy assessments (MoCA, CIBIC-Plus, MMSE, SCOPA-Sleep, NPI, CFI, CGIC-DLB) (unless they have been conducted within past 4 weeks). This change in AChEI medication is considered a protocol deviation and the handling of efficacy data collected after the change of these medications in the efficacy analyses is described in [Section 9.7.1.6](#).

The following restrictions apply to memantine for treatment of DLB (revised per Amendment 03):

- If a subject is already receiving memantine at Screening, they must be on a stable dose for at least 12 weeks before Screening and remain on the same dose during the study until the Follow-Up Visit.
- If a subject is not already receiving memantine at Screening, then this should not have been used at least 12 weeks before Screening and memantine should not be started during the study until the Follow-Up Visit.
- As far as it is feasible subjects who start memantine or change their dose of memantine during the study should undertake an *Unscheduled Visit* before making such changes in their memantine to undertake efficacy assessments (MoCA, CIBIC-Plus, MMSE, SCOPA-Sleep, NPI, CFI, CGIC-DLB) (unless they have been conducted within past

4 weeks). This change in memantine is considered a protocol deviation; the handling of efficacy data collected after the change of these medications in the efficacy analyses is described in [Section 9.7.1.6](#).

The following restrictions apply to medications for Parkinson's disease or motor symptoms of DLB (except CNS-active anticholinergic drugs that are prohibited as above):

- If a subject is already on any of these medications at Screening, then they must be on a stable dose for at least 4 weeks before Screening and remain on the same dose during the study until the Follow-Up Visit.

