- If a subject is not already on any of these medications at Screening, then these should not be started during the study until the Follow-Up Visit.
- Starting or changing the dose of these medications during the study is considered as protocol deviation and the handling of efficacy data collected after the change of these medications in the efficacy analyses is described in [Section 9.7.1.6](#).

The following restrictions apply to medications for antipsychotic or neuroleptic drugs, Yi Gan San, hypnotics, anxiolytics or antidepressants:

- If a subject is already on any of these medications at Screening, then they must be on a stable dose for at least 4 weeks before Screening and remain on the same dose during the study until the Follow-Up Visit.
- If a subject is not already on any of these medications at Screening, then these should not be started during the study until the Follow-Up Visit.
- As far as it is feasible subjects who start or change their dose of these medications should undertake an *Unscheduled Visit* before making such changes in these medications to undertake efficacy assessments (MoCA, CIBIC-Plus, MMSE, SCOPA-Sleep, NPI, CFI, CGIC-DLB) (unless they have been conducted within past 4 weeks). This change in such medications is a protocol deviation and the handling of efficacy data collected after the change of these medications in the efficacy analyses is described in [Section 9.7.1.6](#).

The following restrictions apply to other medications that the subject is taking at Screening or are started during the study:

- These medications may be permitted if they are not included in the prohibited or restricted medications list above, and are considered by the investigator and sponsor medical monitor not to compromise study assessments or subject safety.
- Permitted prior medications should be at a stable dose for at least 4 weeks before Screening and as far as possible remain on the same dose throughout the study.
- Subjects who change the dose of their permitted prior medications or who start permitted new medications during the study may continue in the study if the investigator and sponsor medical monitor consider that this will not compromise study assessments or subject safety.
- As needed (PRN) medications required for performing LP for CSF sampling are permitted in the CSF substudy.

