### **Sensitivity Analysis of Change from Baseline in the MoCA Total Score at 12 Weeks for EMA registration**

A sensitivity analysis will be produced to repeat the primary analysis for MoCA but to censor data after changes in AChEI medications. For this the following missing mechanism will be added to the above reasons in the primary analysis

The effect had rescue medication not been made available to subjects prior to week 12 is not observable for subjects who initiated prohibited or restricted rescue medication. For these subjects, the data collected after initiation of prohibited rescue medication are assumed to contain no treatment effect in the E2027 treatment group. Technically, response data collected after initiation of new AChEIs or after any change in concomitant AChEIs stable dose will be treated as MNAR such that response data treated as MNAR in the E2027 treatment group would be imputed by the mean response in the placebo treatment group as described by the imputation method below.

In order to generate inputs for proposed primary and sensitivity analyses for the EMA registration, a MMRM will be used in separate MMRM analyses for each treatment group for all randomized subjects as well as completers assuming MAR for both treatment groups. The model will be adjusted for baseline MoCA, visit (Week 6 and Week 12), randomization stratification variables (receiving AChEI or not, geographical region [North America, Europe, Japan]), and baseline MoCA  $\times$  visit as fixed effects. An unstructured covariance matrix will be used to model the covariance of within subject effect; if MMRM fails to converge then a covariance structure with fewer parameters from the following list will be employed according to the prespecified order in the list until the MMRM converges. The list of covariance structure will include Heterogeneous Toeplitz, Toeplitz, Heterogeneous

Compound Symmetry, and Compound Symmetry. The Kenward-Roger approximation will be used to estimate the denominator degrees of freedom when unstructured covariance matrix is used. If MMRM fails to converge and a structured covariance matrix is used, the empirical method will be used to compute variance-covariance matrix of the fixed-effects parameters (sandwich estimator). The values of baseline MoCA will be adjusted using the overall baseline mean of all study subjects in computing least square (LS)-means.

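### In the co-primary sensitivity analyses, SAP 5.3.5.1 lets a medication change dated before first dose set the censoring time, which removes every on-treatment value of the affected endpoint

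*SAP*

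**What the plan says.** SAP 5.3.5.1 (Efficacy) defines the dates that drive censoring. For AChEIs, the "date of change in AChEIs stable dose during treatment period, Screening and 12 weeks prior to Screening will be used in the sensitivity analysis"; the purpose is given as "sensitivity analysis to determine the censoring time". For other drugs: "Where non-AChEI restricted medications are changed during the treatment period, Screening and 4 weeks prior to Screening", with 12 weeks for memantine, the method is applied in the same way. A missing change date is imputed with the last visit before the change as the reference date.

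SAP 5.4.1 then uses these dates. The non-EMA sensitivity analyses censor data after the change. In the EMA MoCA sensitivity analysis, response data "after any change in concomitant AChEIs stable dose will be treated as MNAR", and E2027 values treated as MNAR take the placebo mean. The EMA CIBIC-Plus version does the same for AChEI and non-AChEI drugs. Both EMA texts justify this by the effect that would be seen had rescue medication not been available before Week 12.

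SAP 7 and 8.1.4 confine censoring to sensitivity analyses of the co-primary endpoints: MoCA for AChEI changes only, CIBIC-Plus for both classes. Table 4 adds, for CIBIC-Plus, an analysis excluding subjects with changed or new restricted medication. It does not date those changes.

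The look-back lengths match the stability periods in Protocol 9.4.7.2. Subjects not on an AChEI at Screening must also be drug-free: "then these should not have been used for at least 12 weeks before Screening". For Parkinson's drugs and for antipsychotics, Yi Gan San, hypnotics, anxiolytics and antidepressants, a subject "not already on any of these medications at Screening, then these should not be started during the study"; no prior drug-free interval is set.

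**The concern.** The look-back periods are eligibility windows, and here they serve as censoring dates. Censoring for rescue medication should remove data that an intercurrent event after randomization has made uninformative. A change before Screening is not such an event. The analysis baseline is the last pretreatment assessment (SAP 8.1.1), so it is taken after the change, and the subject's medication may be constant for all 12 weeks of treatment. Read literally, data after the change would even include that baseline value.

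What is at stake is a specific check. Protocol 9.7.1.6.1 targets the effect without initiation or dose change of prohibited or restricted drugs. SAP 5.4.1 drops that condition from the co-primary analyses, so the censoring and exclusion analyses are where restricted-medication changes are now examined. If they mix eligibility history with on-treatment rescue, they no longer answer the rescue question. The EMA versions are also pulled toward no effect, because the placebo substitution applies to one arm.

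**Working it through.** The plan states no figure for this issue, so the check is on dates and rules, followed by an illustration of scale.

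**1. Dates.** Screening is Day -42 to Day -8 (SAP 3.2). The look-back can reach Day -42 - 84 = Day -126 (12 weeks) or Day -42 - 28 = Day -70 (4 weeks). All such dates, and any date in Screening, precede Day 1. On-treatment efficacy visits are Week 6 (Day 42) and Week 12 (Day 84), so 2 of 2 fall after the censoring time. For a pre-Screening change the missing-date rule may also fail, since there may be no earlier visit to use as reference.

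**2. What happens to the subject.** In the non-EMA MMRM or GLMM, the subject contributes no post-baseline value of that endpoint. In the EMA versions, an E2027 subject takes the placebo response, while missing placebo values are handled as MAR (SAP 5.4.1).

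**3. Who is caught before Screening** (Protocol 9.3.1 and 9.4.7.2 against SAP 5.3.5.1 and 8.1.4):

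| Class | SAP look-back | Entry rule | Caught before Screening | Endpoint lost |
|---|---|---|---|---|
| AChEI | 12 weeks | stable 12 weeks, or no use for 12 weeks | entry violators only | MoCA, CIBIC-Plus |
| Memantine | 12 weeks | same | entry violators only | CIBIC-Plus |
| Parkinson's drugs; psychotropics | 4 weeks | stable 4 weeks if on the drug at Screening; otherwise no look-back | violators, and possibly eligible subjects who stopped the drug | CIBIC-Plus |

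**4. Does stopping count?** SAP 5.3.5.1 speaks of medications being *changed*, which could include stopping. The EMA CIBIC-Plus text speaks of initiation, or a change in a *concomitant* stable dose. SAP 5.2.5 classes a drug stopped before first dose as *prior*. The three passages do not settle it.

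**5. Scale.** Let p be the share of E2027 subjects caught; p is assumed, as the documents give no count. If these subjects would otherwise show the average effect, placebo-mean substitution gives difference × (1 - p). Approximate power is Φ(Δ / (SD√(2/n)) - 1.96), with SD 3 and n = 80 completers per arm (SAP 4). For the non-EMA column, the same share is dropped from both arms, so n = 80(1 - p).

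| p | 1.4 × (1 - p) | 0.6 × (1 - p) | Power, EMA type (1.4, SD 3) | Power, non-EMA type (1.4, SD 3) |
|---|---|---|---|---|
| 0 | 1.40 | 0.60 | 0.839 | 0.839 |
| 1% | 1.386 | 0.594 | 0.832 | 0.836 |
| 5% | 1.33 | 0.57 | 0.801 | 0.820 |
| 10% | 1.26 | 0.54 | 0.757 | 0.800 |

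These are single-endpoint powers for MoCA; the plan's 80% is for both endpoints jointly.

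For CIBIC-Plus, take the assumed odds ratio 2.607 at a cut where half of placebo subjects lie on the better side (my assumption). The E2027 proportion is 2.607/3.607 = 0.7228. After substitution it is (1 - p) × 0.7228 + p × 0.5, that is 0.7205, 0.7116 and 0.7005 for p = 1%, 5% and 10%. With placebo odds of 1, the odds ratios are 0.7205/0.2795 = 2.58, 0.7116/0.2884 = 2.47 and 0.7005/0.2995 = 2.34.

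**The case against.** The strongest defence is that recent background instability matters. Protocol 9.2 bases the 12-week rule on AChEI efficacy reaching its maximum only after at least 12 weeks, so a change shortly before or during Screening could still move cognition on treatment. That stands as a reason to test robustness. It does not justify this method: a pre-randomization change is a baseline characteristic, which randomization balances between arms in expectation, and nothing about it calls for placebo values in the E2027 arm only.

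It can also be said that one-arm substitution is the declared EMA method for all MNAR data and is conservative for superiority. Both are true. The fault lies in which data are fed into it, and a diluted result could be misread as fragility to rescue medication.

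Three stronger readings are tempting and should not be drawn. A reader might infer that the co-primary result is at risk; SAP 7 leaves those analyses uncensored, and the success rule in SAP 5.3.3 does not use the sensitivity results. A reader might infer that the AChEI window discards eligible subjects; before Screening, the AChEI and memantine windows coincide with the entry rules, so only violators are caught. A reader might take it as settled that an eligible subject who stopped a hypnotic a week before Screening is censored; the wording in SAP 5.4.1 and 5.2.5 points the other way from SAP 5.3.5.1.

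**Conclusion.** The concern holds for the sensitivity analyses of the co-primary endpoints only. As written, a pre-dose change sets the censoring time and removes all on-treatment values of the affected endpoint, contrary to the rescue rationale given for the same analyses. Loss of both visits follows from the stated dates. The size does not: it is about p in the EMA estimates, with p unknown. For MoCA, only AChEI changes count and the entry rule should keep p small, so the 10% row above is an illustration and not an expectation. For CIBIC-Plus, p could extend to eligible subjects if stopping is a change; otherwise it too is limited to entry violations. Memantine and other non-AChEI changes leave MoCA untouched. This should be corrected before unblinding, but it does not threaten the primary conclusion.

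**What to change.** In SAP 5.3.5.1 and 8.1.4, take sensitivity censoring dates only from starts or dose changes of restricted or prohibited medication on or after first dose. Use the same rule for membership of the Table 4 analysis that excludes subjects with changes.

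Report earlier changes that break an entry rule as eligibility deviations. The per-protocol set will not absorb them as it stands: SAP 5.2.3 has no criterion for background-medication stability, and the Version 3 change summary records that the restricted-medication criterion was removed. If robustness to unstable background medication is wanted, add a separate analysis that excludes these subjects in both arms.

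State whether stopping a drug counts as a change, use that meaning in SAP 5.2.5, 5.3.5.1 and 5.4.1, and reconcile it with Protocol 9.4.7.2.

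The cost is SAP wording before unblinding, plus a clarifying sentence in the protocol if the reconciliation needs one. No new data are required. The downside is that the censoring analysis will no longer cover pre-dose instability; the separate exclusion analysis would.

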#### 5.3.5.2 Safety

The methods for handling missing start and end dates are described in standard Eisai SDTM Domain Mapping Specifications Template (Appendix 13.4) and documented in SDTM+ specification.

All the listings will display the original missing values.

### 5.3.6 Other Considerations

Not Applicable.

## 5.4 Efficacy Analyses

### 5.4.1 Primary Efficacy Analyses

The treatment effect of interest will be the efficacy as measured by co-primary endpoints that would be observed at 12 weeks regardless of whether or when the assigned treatment was discontinued due to adverse event, lack of efficacy or any other events related to treatment or

study outcome. The target population is DLB subjects defined by inclusion/exclusion criteria.

There are 2 co-primary efficacy endpoints, change from baseline in the MoCA total score at 12 weeks and CIBIC-Plus scale at 12 weeks. Overall there are 2 null hypotheses ( $H_0$ ) to be tested in the primary analysis:

$H_{01}$ : There is no difference in the mean change from baseline in the MoCA total score at 12 weeks between E2027 and placebo.

$H_{02}$ : The proportional odds ratio based on CIBIC-Plus scale at 12 weeks between E2027 and placebo is equal to 1.

The corresponding 2 alternative hypotheses are that there is a difference in the mean change from baseline in MoCA total score at 12 weeks in this co-primary endpoint between E2027 and placebo and the proportional odds ratio based on CIBIC-Plus scale at 12 weeks between E2027 and placebo is not equal to 1. The study will be considered positive if statistically significant improvement (at level of 0.05 (2-sided) or 0.025 (1-sided)) is observed in both co-primary endpoints in E2027.

Due to correspondence with the FDA during the study, separate analyses will be performed for the non-EMA and EMA registrations, the endpoints remain identical.

### **Non-EMA Analyses**

#### **Co-primary Analysis of Change from Baseline in the MoCA Total Score at 12 Weeks for non-EMA registration**

Change from baseline in the MoCA total score at 12 weeks will be analyzed using MMRM. The MMRM model will include baseline variable (corresponding to the response variable in the model) as a covariate, treatment group, visit (Week 6 and Week 12), randomization stratification variables (receiving AChEI or not, geographical region [North America, Europe, Japan]), baseline variable-by-visit interaction, and treatment group-by-visit interaction as fixed effects. An unstructured covariance matrix will be used to model the covariance of within subject effect; if MMRM fails to converge then a covariance structure with fewer parameters from the following list will be employed according to the prespecified order in the list until the MMRM converges. The list of covariance structure will include Heterogeneous Toeplitz, Toeplitz, Heterogeneous Compound Symmetry, and Compound Symmetry. The Kenward-Roger approximation will be used to estimate the denominator degrees of freedom when unstructured covariance matrix is used. If MMRM fails to converge and a structured covariance matrix is used, the empirical method will be used to compute variance-covariance matrix of the fixed-effects parameters (sandwich estimator).

#### **Sensitivity Analysis of Change from Baseline in the MoCA Total Score at 12 Weeks for non-EMA registration**

A sensitivity analysis will be produced to repeat the primary analysis for MoCA but to censor data after changes in AChEI medications.

### **Co-primary Analysis of the CIBIC-Plus Scale at 12 Weeks for non-EMA registration**

CIBIC-Plus scale at 12 weeks will be analyzed using GLMM. The GLMM model will include treatment, visit, randomization stratification variables (receiving AChEI or not, geographical region [North America, Europe, Japan]), and treatment x visit as fixed effects. The model will be fitted using GLMM with a multinomial distribution and a cumulative logit link function. If the proportional odds assumption is contradicted ( $p < 0.05$  in Score Test for the Proportional Odds Assumption) by the observed data in either the entire population or any stratum, the GLMM method will be replaced by the nonparametric van Elteren test adjusting 2 randomization stratification variables (on stabilized AChEI dose or not; geographical region [North America, Europe, Japan]).

### **Sensitivity Analysis of the CIBIC-Plus Scale at 12 Weeks for non-EMA registration**

A sensitivity analysis will be produced to repeat the primary analysis for CIBIC-Plus but to censor data after changes in both AChEI and non-AChEI medications.

